**3. Outcome Measures**

Every participant in the study population underwent obstetric ultrasound examination and fetal-maternal assesment was carried out by one of the investigators. The obstetric anamnesis were obtained from all participants. The demographic data like age, gravidity, parity, body mass index (BMI) and gestational age were recorded. The gestational age was determined by calculation from the last menstrual period and supported by the ultrasonography measurements at first trimester of gestation. Maternal venous plasma samples were taken for measurement of cadmium, lead and vanadium levels after the diagnosis of L-PrE in outpatient clinic. These samples quickly centrifuged at 1,500 g for 10 min, plasma samples were seperated and stored at -80 C until the day of measurement. All patients with L-PrE were also hospitalized and their pregnancies were terminated. The samples of the control groups were obtained during the routine obstetrical care examination in the third trimester of pregnancy. Then, these pregnant women were followed-up until the delivery. Both groups were compared in terms of maternal age, BMI, week of gestation, gravida, parity, live born, systolic/diastolic blood pressure, total protein in spot urine sample, hemoglobin, hematocrit, platelet count, white blood cell count, urea, uric acid, albümin, blood urea nitrogen, creatinine, liver function tests (AST, ALT), lactic acid dehydrogenase, cadmium, lead and vanadium concentrions and infant weight at delivery. Small for gestational age (SGA) neonate was defined as birth weight <10th percentile for gestational age with Turkey's national nomogram as the reference for fetal growth. The samples were transferred within boxes in ice molds to Yozgat Bozok University Science and Technology Application and Research Center (Occupational and Environmental Toxicology Laboratory) for measuring heavy metal and trace element levels. The frequency of seafood consumption was divided into four categories: 2-3 per week, 1-2 per week, 1-2 per month, and rare. Smoking was classified into 3 groups (none, formerly smoker, and active smoking). Passive smoking was also categorized into 2 groups (no and yes). The education levels was classified into 4 groups (illiterate,

primary education, high school, and university). The residences of women was classified as rural and urban. Furthermore, the residences of women have divided either living near a busy street (around 100 metres) or not.

Venous blood sampled from the antecubital veins for measuring plasma concentration of cadmium, lead and vanadium levels. The three metals (cadmium, lead and vanadium) were measured using inductively coupled plasma-mass spectrometry (Thermo Scientific ICAPQc, USA).

#### **4. Endpoints of the study:**

The primary outcome in these analyses was to compare cadmium, lead and vanadium levels in L-PrE group and control group.

The secondary outcome was to compare the cadmium, lead and vanadium levels in mild L-PrE group and severity L-PrE group.

Tertiary outcome was to compare the cadmium, lead and vanadium levels in SGA group and non-SGA group.

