### **1. Participant Flow**

#### **Recruitment Details**

This observational case-control study was conducted at the Department of Obstetrics and Gynecology, Cengiz Gokcek Public Hospital, Gaziantep, Turkey, between March 2018 and June 2019. The protocol was approved by the Ethics Committee for Clinical Research of Gaziantep University (reference no: 2019/36). The investigators included subjects consisted of women with a singleton pregnancy who were diagnosed as having late-onset preeclampsia between 34+0 and 41+0 weeks of gestation. Pregnant women with uncomplicated pregnancies were randomly selected to serve as controls. The study was conducted with 46 late-onset preeclampsia patients as study group and 46 patients with normal pregnancies as control group. All participants included in the study gave oral and written informed consent.

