**2. Baseline Characteristics**

To detect significant difference between groups according to lead levels with a moderate effect size (Cohen's  $d = 0.62$ ), minimum required sample size was estimated as 42 for each group ( $\alpha=0.05$ ,  $1-\beta=0.80$ ). Power analysis was performed by using G power package version 3.1. Kolmogorov Smirnov and Shapiro Wilk tests were used to test the normal distribution of data. For comparing groups (L-PrE/control) the student t-test was used for variables that have a normal distribution, and the Mann Whitney U test was used for variables that have not a normal distribution. The ROC analysis was applied for the determination of cut-off point for vanadium variable. Moreover, Spearman correlation test was used for the relationship of between variables. SPSS for Windows 22.0 and Medcalc programs were used for statistical analysis.  $p<0.05$  was accepted as statistical significance.

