#### **5. Limitations and strengths:**

Our study has some limitations. Firstly, none of these patients had ever been occupationally exposed to these three metals. Further, the city in which the study was performed is far from the coast.

Therefore, the participants' seafood consumption was very low or absent because of the low socio-economic level. Furthermore, our population in this study are more illiterate than others. Because of these reasons, the sample size of the population may not reflect the population in general. Second, the blood samples in the study were only collected at a single time point which may reflect the three metals exposure levels only recent exposure, not before and during pregnancy, and also limiting the ability to establish temporality. Third, it could be even better to measure urinary levels of the metals. Lastly, because our study is observational, we could not eliminate the possibility of unmeasured and/or residual confounding of the reported associations. On the contrary, some confounding factors which are considered as risk factors for PrE and metals exposure are either nearly equally distributed or absent in our patient population. For example, patients with pre-pregnancy systemic diseases, advanced maternal age, multifetal gestation were excluded. Nulliparity, increased body mass index and sociodemographic characteristics such as smoking and traffic exposure of the two groups are similar.

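### Three unranked metals form the primary outcome and each is judged at p<0.05; if any one significant metal counts, the chance of a false positive is about 10–14% (correlations 0 to 0.8), not 5%

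*Protocol*

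**What the plan says.** Protocol, section 4 (Endpoints of the study), lists the three metals together: "The primary outcome in these analyses was to compare cadmium, lead and vanadium levels in L-PrE group and control group". No metal comes first, and there is no rule for combining the three results.

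The statistical methods are in section 2 (Baseline Characteristics). Each variable gets its own two-group test: Student's t-test if its distribution is normal; otherwise, "the Mann Whitney U test was used for variables that have not a normal distribution". A p-value below 0.05 "was accepted as statistical significance". This is the only threshold given, and the section mentions no adjustment for several tests.

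The sample size in the same section is tied to one metal: "To detect significant difference between groups according to lead levels with a moderate effect size" (Cohen's d = 0.62, α = 0.05, power 0.80), "minimum required sample size was estimated as 42 for each group". Yet the ROC cut-off analysis in that section is for vanadium, so the text does not consistently point to one principal metal.

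Section 1 (Recruitment Details) gives the numbers achieved: "The study was conducted with 46 late-onset preeclampsia patients as study group and 46 patients with normal pregnancies as control group".

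**The concern.** A 5% threshold limits the error of one test. Here the primary outcome is a set of three tests, and the error rate of the set depends on how the three results are combined. The protocol leaves that open, and the two obvious rules have different consequences:

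- **Any one metal suffices.** There are three chances of a false positive, so the set's error rate exceeds 5%.
- **All three metals are required.** The error rate stays at or below 5%, but the power is that of passing three tests, which is lower than the power of one.

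The practical risk is narrow. A single metal with p between 0.05/3 = 0.0167 and 0.05 could be reported as a positive primary finding although the false-positive rate across the three metals is not held at 5%. Also, the stated 80% power could be taken to cover the whole primary outcome, when it was worked out for lead only.

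**Working it through.** **Inputs from the protocol.** Three primary comparisons (section 4); threshold 0.05, t-test or Mann-Whitney U, d = 0.62 for lead, power 0.80, 42 per group (section 2); 46 per group recruited (section 1).

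**Assumptions, because the protocol gives no figure.** A common within-group correlation ρ between the metals, and d = 0.62 for cadmium and vanadium where all three are considered. Tests are taken as two-sided, which is what reproduces the stated sample size.

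**1. The plan's own figure.** A two-sided two-sample t-test with d = 0.62, α = 0.05 and power 0.80 (noncentral t) needs 41.8, so 42 per group; power at 42 is 0.802. The stated 42 is correct. A one-sided test would need 33, which does not match.

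**2. Any-metal rule, independent metals.** P(at least one false positive) = 1 − (1 − 0.05)³ = 1 − 0.857375 = 0.1426, or 14.3%. Under any dependence it cannot exceed 3 × 0.05 = 15%.

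**3. Correlated metals.** Simulation with 46 per group and normal data, t-tests unless marked:

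| ρ | Any false positive at 0.05 | Same, Mann-Whitney | Same, Holm (t-test) | Power, all three p<0.05, d = 0.62 each |
|---|---|---|---|---|
| 0 | 14.2% (exact 14.3%) | 14.6% | 4.8% | 58.4% (exact 58.6%) |
| 0.3 | 13.8% | 13.7% | 4.8% | 63.5% |
| 0.5 | 12.5% | 12.9% | 4.4% | 67.0% |
| 0.8 | 9.9% | 10.3% | 3.5% | 73.8% |

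At higher correlations the any-metal error falls further: 8.4% at 0.9 and 6.0% at 0.99 (z-tests). The choice between t-test and Mann-Whitney makes little difference to the error rate.

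**4. All-metals rule.** With independent metals the power is 0.837³ = 0.586; the last column gives the correlated cases. It does not stay below 80% at every correlation: it is about 81% at ρ = 0.98.

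**5. Power for lead at 46 per group, d = 0.62.**
- t-test: 0.837 at α = 0.05; 0.703 at α = 0.05/3.
- Mann-Whitney, normal data: about 0.82 and 0.67–0.68. At the lower bound of its relative efficiency for location shifts (0.864): 0.779 and 0.625.

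Holm's first step uses 0.05/3, so 70% is the lower limit of the t-test power for lead under Holm, reached when only lead differs. If all three metals have d = 0.62, Holm power for lead is about 80% at ρ = 0 and 77% at ρ = 0.8.

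**The case against.** The strongest objection is that an adjustment or a success rule is often left to the statistical analysis plan, which may exist and is not shown. A reader might infer that no adjustment was ever planned; the protocol cannot support that. But the point does not rest on the silence alone. Section 2 is itself a statistical methods paragraph: it fixes the tests, the threshold and the sample size, and section 4 fixes three unranked primary comparisons. As written, these do not give the primary set a 5% error rate under the any-metal reading.

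A second objection is that the protocol never adopts that reading. It speaks only of comparing levels, and in an observational case-control study three separate questions, each at its own 5%, is a common approach. This stands as a limit on the claim. A reader might infer that the study's error rate simply is 14%. That does not follow: the figure depends on the any-metal rule, which the protocol neither adopts nor excludes, and on the correlation. Still, the protocol does name a primary outcome, a power calculation and a significance threshold, so how a significant metal will be interpreted is a fair question.

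A third objection is that sizing on lead makes lead the principal metal. The endpoint text does not say so, and the ROC analysis singles out vanadium.

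**Conclusion.** The point holds in conditional form, at minor to moderate severity. If any one significant metal is read as a positive primary result, the chance of at least one false positive is 14.3% for independent metals and about 10–14% for correlations of 0 to 0.8; above about 0.8 it falls below 10%. If all three must be significant, error is controlled, but power at 46 per group is about 59–74% over correlations 0 to 0.8, assuming d = 0.62 for every metal. The correlations, and the effect sizes for cadmium and vanadium, are assumptions.

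Two stronger conclusions are not supported. The sample size is not wrong: 42 per group reproduces for one two-sided t-test of lead, and 46 exceeds it. Nor are the data invalid: each test keeps its 5% error taken singly, and what needs settling is how the three are read together.

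**What to change.** State in the protocol or study report:

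- The primary outcome comprises three comparisons (cadmium, lead, vanadium; L-PrE versus control). Holm-adjusted p-values (familywise two-sided 0.05) are reported beside the unadjusted ones, and any claim of a positive primary result rests on the adjusted values.
- When the adjustment was specified. Label it post hoc unless a record made before the results shows that it was planned. By the same test, lead may be named the single primary metal only if such a record shows that intent.
- The sample size was calculated for lead only (t-test, d = 0.62), and no power is reported for cadmium, vanadium or the three metals together. With 46 per group, t-test power for lead is 84% at 0.05 and at least about 70% under Holm. If lead is analysed by Mann-Whitney, the corresponding figures with normal data are about 82% and 67–68%.

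The cost is wording and the adjustment of three p-values, with no added patients. The downside is a stricter threshold for the primary claim, a slightly less favourable stated power and possibly a post hoc label.

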#### **5. Limitations and strengths:**

Our study has some limitations. Firstly, none of these patients had ever been occupationally exposed to these three metals. Further, the city in which the study was performed is far from the coast.

Therefore, the participants' seafood consumption was very low or absent because of the low socio-economic level. Furthermore, our population in this study are more illiterate than others. Because of these reasons, the sample size of the population may not reflect the population in general. Second, the blood samples in the study were only collected at a single time point which may reflect the three metals exposure levels only recent exposure, not before and during pregnancy, and also limiting the ability to establish temporality. Third, it could be even better to measure urinary levels of the metals. Lastly, because our study is observational, we could not eliminate the possibility of unmeasured and/or residual confounding of the reported associations. On the contrary, some confounding factors which are considered as risk factors for PrE and metals exposure are either nearly equally distributed or absent in our patient population. For example, patients with pre-pregnancy systemic diseases, advanced maternal age, multifetal gestation were excluded. Nulliparity, increased body mass index and sociodemographic characteristics such as smoking and traffic exposure of the two groups are similar.

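### Confounding by smoking and traffic exposure is offset by an unquantified claim that the groups are similar, which 46 women per group cannot support, while the stated metal comparison is unadjusted

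*Protocol*

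**What the plan says.** Group sizes and selection (Protocol, Recruitment Details): "The study was conducted with 46 late-onset preeclampsia patients as study group and 46 patients with normal pregnancies as control group". On the controls: "Pregnant women with uncomplicated pregnancies were randomly selected to serve as controls". No matching on any exposure is described.

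Exposures recorded (section 3, Outcome Measures): "Smoking was classified into 3 groups (none, formerly smoker, and active smoking"; passive smoking as yes or no; and "the residences of women have divided either living near a busy street (around 100 metres) or not". No counts are given for any of these.

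Analysis (section 2, Baseline Characteristics): "the student t-test was used for variables that have a normal distribution, and the Mann Whitney U test was used for variables" that are not normally distributed. Both are unadjusted two-group tests. The study is sized on lead: "To detect significant difference between groups according to lead levels with a moderate effect size" (d = 0.62), for which "minimum required sample size was estimated as 42 for each group".

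Confounding (section 5, Limitations and strengths): the text first grants that unmeasured or residual confounding cannot be ruled out. It then turns the other way. Some factors, which it describes as bearing on both preeclampsia and metal exposure, are said to be almost evenly distributed or absent, and "sociodemographic characteristics such as smoking and traffic exposure of the two groups are similar".

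**The concern.** By the document's own account, smoking and traffic exposure can affect both sides of the primary comparison, which is metal levels in late-onset preeclampsia against controls (section 4, Endpoints of the study). The protection it states for these two exposures is the claim of similarity. Drawing controls at random from uncomplicated pregnancies does not supply that protection. It makes them representative of such pregnancies, but it does not balance exposures between cases and controls as random allocation would.

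An imbalance that goes unnoticed in groups of this size passes straight into an unadjusted difference. More exposed women among the cases would look like an association between the metal and preeclampsia; more among the controls could hide a real one. The variables needed to deal with this were recorded, but in the section on confounding they serve only to reassure.

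**Working it through.** **Inputs from the Protocol.** 46 per group; d = 0.62 for lead, alpha 0.05, power 0.80, 42 per group; smoking in three categories, passive smoking and busy-street residence as yes/no.

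**Inputs assumed, because the Protocol gives none.** Proportion exposed in the less exposed group: 10–50%. Effect of exposure on a metal: 1 SD, range 0.5–1.5.

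**1. The plan's own figure.** Normal approximation, two-sided: n = 2(1.960 + 0.842)² / 0.62² = 40.8, so 41 per group. The noncentral t calculation gives 41.8, so 42. The stated figure reproduces. At 46 per group, power for d = 0.62 is 83.7%.

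**2. How large a gap can stay non-significant.** Pearson chi-square without continuity correction, 46 v 46; for each starting count, the largest gap with p ≥ 0.05:

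| Base rate (about) | Counts | Gap (points) | p |
|---|---|---|---|
| 10% | 5 v 12 | 15 | 0.060 |
| 20% | 9 v 17 | 17 | 0.064 |
| 30% | 14 v 23 | 20 | 0.056 |
| 50% | 23 v 32 | 20 | 0.056 |

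Example, second row: 92 × (9×29 − 37×17)² / (46×46×26×66) = 3.43, p = 0.064. One more exposed woman, 9 v 18, gives p = 0.039, so a 20-point gap stays non-significant only when the exposure is common (about 30% or more). Fisher's exact test gives larger p-values for the same tables (0.105, 0.104, 0.088, 0.088), so the uncorrected chi-square is the stricter choice here.

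**3. Power to see an imbalance.** For 20% v 35% with 46 per group, power is 36%. From a 20% base rate, 80% power needs about 46–47% in the other group, depending on the variance formula.

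**4. Shift in the metal difference.** Shift (SD) = gap × effect of exposure (SD).

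| Gap | Effect 0.5 SD | Effect 1 SD | Effect 1.5 SD |
|---|---|---|---|
| 10 points | 0.05 | 0.10 | 0.15 |
| 17 points | 0.085 | 0.17 | 0.255 |
| 20 points (common exposures only) | 0.10 | 0.20 | 0.30 |

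Against d = 0.62: 0.05/0.62 = 8%; 0.10/0.62 = 16%; 0.17/0.62 = 27%; 0.255/0.62 = 41%. For 20 points: 0.20/0.62 = 32% (range 16–48%).

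**5. False-positive rate if the true difference is zero and such a shift is present.** Noncentral t, 90 degrees of freedom, nominal 5% two-sided: a shift of 0.10 SD gives 7.6%, 0.15 SD gives 11%, and 0.20 SD gives 16%.

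**The case against.** **The text admits confounding.** The claim of similarity comes in a limitations section, after a plain concession. A reader might infer that the document treats confounding as dealt with. It does not; similarity is offered as a counterweight for named factors. This part of the objection stands.

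**Only smoking and traffic are at issue.** A reader might extend the point to every background source of metals. The text does not support that. Seafood intake is described as very low or absent and occupational exposure as never present, both as limits on generalising the results. This also stands.

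**No test is cited for similarity.** The Protocol names no test for categorical data and does not say that similarity was judged at p < 0.05. The chi-square tables therefore show what a sample of this size could rule out, not what was done. This stands as well, but any other criterion is equally unstated, and the claim remains without figures.

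**No imbalance is shown.** That is correct. The exposure counts are not given, the effect sizes are assumed, and the 0.62 benchmark applies to lead only. One modest imbalance would not produce the whole of 0.62 SD, although several in the same direction would add up.

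**Adjustment may be left to the SAP.** The SAP is not shown, so the lack of an adjusted model is not in itself a finding. What can be faulted is what the Protocol states: an unadjusted comparison, with a similarity claim as the offset for two exposures that it describes as bearing on both outcome and metal levels.

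**Conclusion.** The point holds in a limited form. The similarity statement for smoking and traffic has no numbers behind it, and at 46 per group a non-significant comparison would be compatible with gaps of about 15–17 points at base rates of 10–20%, or about 20 points at 30–50%. On the assumed effect of 1 SD, a gap of 10–17 points moves the metal difference by 0.10–0.17 SD. With effects of 0.5–1.5 SD the range is 0.05–0.26 SD, about 8–41% of the planned effect for lead. A gap of 20 points, possible only for common exposures, moves it by 0.20 SD (range 0.10–0.30).

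These are possible biases and rest on assumed exposure effects. The document does not show that the groups differ, nor that any reported metal difference is explained by smoking or traffic. The analysis and the wording should be changed, but the point does not invalidate the comparison.

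**What to change.** 1. For each metal, report the late-onset preeclampsia minus control difference with its confidence interval from a linear model (log scale if the metal is skewed) containing active smoking (current or not), passive smoking and busy-street residence. Place it beside the unadjusted result. If this model was not pre-specified, label it as added after data collection, since recruitment ended in June 2019.
2. Tabulate these three exposures by group with counts and standardised differences, so that readers can judge balance without relying on a significance test.
3. Reword section 5 so that similarity is no longer offered as an offset to confounding by smoking and traffic; refer instead to the table and the adjusted estimates.

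Cost: one regression per metal on data already recorded, three degrees of freedom out of 92 women (residual 90 − 3 = 87), and possibly a smaller or less precise reported difference. Keeping former smokers as a separate category would use one more degree of freedom. Coarse exposure categories will still leave some residual confounding, which the existing concession in section 5 already covers.
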